## 9.1 Study design Part 1 (completed)

In order to assess the first two objectives, the **co-primary objective** is to determine a range of optimal combination therapies, among the combinations provided in the following table where an optimal combination is a combination that is estimated to have an acceptable toxicity profile as measured by DLT's and a high rate of immunologic response (IRR) as measured by peak immune response.

**Arm/Combination** Zone Peptide vaccine Adjuvant preparation LPV7 + tet 1 **IFA** Α В LPV7 + tet PolyICLC 1 С LPV7 + tet Resiguimod 1 2 D LPV7 + tet PolyICLC + Resiguimod 2 Ε LPV7 + tet IFA + PolyICLC 2 IFA + Resiquimod F LPV7 + tet IFA + PolyICLC + Resiguimod 3 G LPV7 + tet

Table 14: Study Design

DLTs are defined in Section 7.8 of the protocol.

Within the range of optimal doses a **co-primary objective** is if more than one combination is contained within the range of optimal combinations, to estimate the difference in immunologic response rates between combinations, among those in the range of optimal combinations.

# 9.2 Combination allocation Part 1 (completed)

The goal is to determine the range of optimal combinations, where optimal combination allocation will occur in two stages. The initial stage will accrue eligible participants in cohorts of one on each arm per the allocation process in 9.2.1 until a participant experiences a DLT. The second stage will allocate eligible participants based upon a continual reassessment method (CRM) for combinations of agents. Randomization will be based on equal allocation among allowable arms unless a weighted allocation scheme is triggered (Section 9.2.1). Randomization will not be stratified by institution. Participants must be observed for a minimum of 3 weeks after the initial vaccine for initial escalation between zones, and between the 1st and 2nd participants within an arm.

## 9.2.1 Combination allocation in Stage 1:

The initial stage will accrue eligible participants on combinations in cohorts of one until a participant experiences a dose-limiting toxicity (DLT). The escalation plan for the first stage is based on grouping treatment combinations into "zones." With this dose escalation design participants can be accrued and assigned to other open combinations within a zone but escalation will not occur outside the zone until the minimum follow-up period is observed for the first participant accrued to a combination. Allocation will begin in Zone 1.

#### Allocation in Zone 1:

- a) The first eligible participant in Zone 1 will be entered onto combination A, B or C, chosen at random.
- b) The second eligible participant in Zone 1 will be randomized to one of the two remaining combinations in the zone that have not yet been tried.
- c) The third eligible participant will be entered onto the combination in Zone 1 that has not yet been tried.
- d) Escalation to a Zone 2 occurs only when all combinations in Zone 1 have accrued at least 1 participant and no participants have experienced a DLT.

### Allocation in Zone 2:

- a) After completion of Zone 1, the first eligible participant in Zone 2 will be entered onto combination D, E or F, chosen at random.
- b) The second eligible participant in Zone 2 will be randomized to one of the two remaining combinations in the zone that have not yet been tried.
- c) The third eligible participant will be entered onto the combination in Zone 2 that has not yet been tried.
- d) Escalation to a Zone 3 occurs only when all combinations in Zone 2 have accrued at least 1 participant and no participants have experienced a DLT.

#### Allocation in Zone 3:

- a) Note Zone 3 contains a single combination, so the first eligible participant on Zone 3 will be entered onto combination G.
- b) If 0/1 participants experience a DLT, the next eligible participant will be entered onto combination G. If 0/2 participants experience DLT, the next eligible participant will be randomized to any combination.
- c) In the absence of DLTs, participants will continue to be randomized to combination A through G until a DLT occurs (upon which the modeling stage begins), or until at least 3 participants have been treated at every combination, at which point allocation will be based on which combination has the highest IRR. In the absence of DLTs, participants will continue to be entered on the combination with the highest IRR until sufficient information has been obtained regarding the

optimal combination, according to the stopping rules described below. Once a DLT has been observed, Stage 2 using CRM modeling begins.

# 9.2.2 Combination allocation in Stage 2:

The second stage will allocate eligible participants based upon a continual reassessment method for combinations of agents (R package, pocrm). The modeling stage uses (a) a selected set of possible orderings for the DLT probabilities and (b) a working model for the DLT probabilities under each ordering.

Table 15: Possible Orderings of DLT Probabilities

Possible orderings of DLT probabilities				
1) A-B-C-D-E-F-G				
2)	A-C-B-D-F-E-G			
3)	B-A-C-E-D-F-G			
4)	B-C-A-E-F-D-G			
5)	C-A-B-F-D-E-G			
6)	C-B-A-F-E-D-G			

Table 16: Working Model of DLT Probabilities Under Each Ordering

	Working model of DLT probabilities under each ordering**								
Order	Α	В	С	D	E	F	G		
1	0.01	0.05	0.12	0.20	0.28	0.36	0.45		
2	0.01	0.12	0.05	0.20	0.36	0.28	0.45		
3	0.05	0.01	0.12	0.28	0.20	0.36	0.45		
4	0.12	0.01	0.05	0.36	0.20	0.28	0.45		
5	0.05	0.12	0.01	0.28	0.36	0.20	0.45		
6	0.12	0.05	0.01	0.36	0.28	0.20	0.45		
**Working	models wer	e chosen a	accordina t	o the algori	thm of Lee	and Cheur	na (2009)		

Within each ordering, the continual reassessment method (CRM) is fit, using the working model and the accumulated data. The second stage will accrue eligible participants in cohorts of one and use a CRM model fit to estimate DLT probabilities at each arm combination. For each order,  $m=1,\cdots,6$ , in Table 16, the DLT probabilities for each arm  $i = 1, \cdots, 7,$ modeled via combination are а one-parameter pow er  $Pr({\sf DLT} \ {\sf at\ combination}\ i) pprox p_{mi}^{\theta_m}$  , where the  $p_{mi}$  are the working model values for order mgiven in Table 16. After accrual of each participant into the trial, the parameter  $\theta_m$  is estimated for each ordering by maximum likelihood estimation where the likelihood is given by  $\prod_{i=1}^{7} \left(p_{mi}^{\theta_m}\right)^{y_i} \left(1 - p_{mi}^{\theta_m}\right)^{n_i - y_i}$  where  $y_i$ = the number of DLTs and  $n_i$ =the number of treated participants in arm combination i. The order with the largest likelihood is chosen and within this ordering, DLT probability estimates are updated for each combination. If there is a tie between the likelihood values of two or more orderings, then the selected order is randomly chosen from among the tied orderings. These DLT probabilities will be used to define a set of "acceptable" combinations, defined as any dose with estimated DLT probability less than or equal to 33%. This toxicity tolerance of 33% was chosen based on the expectedness of adverse events.

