#### Part 2:

The peptides will be prepared by combining the LPV6 mixture of 6 peptides with one NY-ESO-1 long peptide. The long melanoma peptides (LPV6) will be available as single-use vials of 1 ml volume containing 600 mcg/ml of each peptide. The NY-ESO-1 peptide is provided as lyophilized preparation with 600 mcg of peptide in single use vials. For each vaccine, the full 1 ml of the peptide solution of LPV6 (600 mcg) will be withdrawn and injected into the vial of lyophilized NY-ESO-1 peptide, creating a solution/suspension of all 7 long peptides, each at 600 mcg/ml. Then 0.75 ml of this solution/suspension (450 mcg of all 7 long peptides) will be withdrawn into a syringe for injection as specified below for each study arm. Details of making emulsions with IFA (Montanide ISA-51) are provided in the Investigator's Brochure and Study Manual.

**Study Arm A (IFA)**: Sterile saline solution 0.75ml will be added to 0.75 ml of LPV7 + tetanus peptide (total 1.5 ml). This will be combined with 1.5 ml of Montanide ISA-51VG to create an emulsion. Two (2) ml will be injected half-intradermally and half-subcutaneously in one skin location.

**Study Arm B (polyICLC)**: PolyICLC (Hiltonol) is provided from Oncovir, Inc. (Washington, D.C.) as a clinical grade reagent for experimental use in single-use vials containing 1 mL of a 2 mg/mL solution. We will administer 1 mg (0.5 ml) per vaccine. PolyICLC (Hiltonol) 0.75 ml will be added to 0.75 ml of LPV7 + tetanus peptide. One (1) ml of this will be injected half-intradermally and half-subcutaneously in one skin location.

**Study Arm C (resiquimod)**: Resiquimod is provided by 3M (Minneapolis, MN) and is packaged in multi-dose tubes (typically 3 g of 0.2% gel). Sterile saline solution 0.75ml will be added to 0.75 ml of LPV7 + tetanus peptide. One (1) ml of this will be injected half-intradermally and half-subcutaneously in one skin location. Immediately after vaccine injection, apply approximately 500 mg of 0.2% resiquimod gel with a gloved finger over a 25 cm² area of the skin at the vaccine site. Rub the gel into the skin for 1 minute until it vanishes. Following application, the site may be covered with an occlusive dressing, such as Tegaderm, for about 8 hours. Participants are encouraged to wash the area at 8 hours after application.

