**Study Arm D (polyICLC + resiquimod)**: PolyICLC (Hiltonol) 0.75 ml will be added to 0.75 ml of LPV7 + tetanus peptide. One (1) ml of this will be injected half-intradermally and half-subcutaneously in one skin location Immediately after vaccine injection, apply approximately 500 mg of 0.2% resiquimod gel with a gloved finger over a 25 cm² area of the skin at the vaccine site. Rub the gel into the skin for 1 minute until it vanishes. Following application, the site may be covered with an occlusive dressing, such as Tegaderm, for about 8 hours. Participants are encouraged to wash the area at 8 hours after application.

**Study Arm E (IFA + polyICLC):** Part 1: PolyICLC (0.75 ml) will be added to 0.75 ml of LPV7 + tetanus peptide (total 1.5 ml). This will be combined with 1.5 ml of Montanide ISA-51VG to create an emulsion. Two (2) ml will be injected half-intradermally and half-subcutaneously in one skin location.

Study Arm E2 (IFA + polyICLC): Part 2: PolyICLC (0.75 ml) will be added to 0.75 ml of LPV7 (total 1.5 ml). This will be combined with 1.5 ml of Montanide ISA-51VG to create an emulsion. Two (2) ml will be injected half-intradermally and half-subcutaneously in one skin location (as in study arm A).

Study Arm F (IFA + resiquimod): Sterile saline solution 0.75ml will be added to 0.75 ml of LPV7 + tetanus peptide (total 1.5 ml). This will be combined with 1.5 ml of Montanide ISA-51VG to create an emulsion. Two (2) ml will be injected half-intradermally and half-subcutaneously in one skin location (as in study arm A). Immediately after vaccine injection, apply approximately 500 mg of 0.2% resiquimod gel with a gloved finger over a 25 cm² area of the skin at the vaccine site. Rub the gel into the skin for 1 minute until it vanishes. Following application, the site may be covered with an occlusive dressing, such as Tegaderm, for about 8 hours. Participants are encouraged to wash the area at 8 hours after application.

Study Arm G (IFA + polyICLC + resiguimod): PolyICLC (0.75 ml) will be added to 0.75 ml of LPV7 + tetanus peptide (total 1.5 ml). This will be combined with 1.5 ml of Montanide ISA-51VG to create an emulsion. Two (2) ml will be injected half-intradermally and half-subcutaneously in one skin location (as in study arm A). Immediately after vaccine and polyICLC injection, apply approximately 500 mg of 0.2% resiguimod gel with a gloved finger over a 25 cm² area of the skin at the vaccine site. Rub the gel into the skin for 1

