## 9.3 Statistical properties Part 1 (completed)

Simulation results were run (R package, pocrm) to display the performance of the design characteristics. For each scenario, 1000 simulated trials were run. Each table reports the true DLT probability at each combination, the true IRR at each combination, the percentage of trials in which each combination was recommended as the optimal combination, and the average number of participants treated in a simulated study.

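### In four of the six DLT orderings in Table 15 the IFA-free pair (Arm D) sits opposite to where its components would place it, and no simulated scenario tests this; a labelled sensitivity refit is needed

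*Combined protocol and SAP*

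**What the plan says.** Section 5.2.1 defines the arms. The single-adjuvant labels begin "Study Arm A (IFA", "Study Arm B (polyICLC" and "Study Arm C (resiquimod"; the pair labels begin "Study Arm D (polyICLC + resiquimod", "Study Arm E (IFA + polyICLC" and "Study Arm F (IFA + resiquimod". Tables 1A and 14 agree. So D = B+C, E = A+B, F = A+C, and G contains all three.

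For Stage 2, Section 9.2.2 says: "The modeling stage uses (a) a selected set of possible orderings for the DLT probabilities". Table 15 lists six orderings and Table 16 assigns the working values 0.01, 0.05, 0.12, 0.20, 0.28, 0.36 and 0.45 along each. A one-parameter power model is fitted by maximum likelihood under each ordering, and the ordering with the largest likelihood is used. Arms with an estimated DLT probability of at most 33% are acceptable.

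On operating characteristics, Section 9.3 says: "For each scenario, 1000 simulated trials were run". There are four scenarios (Tables 17 to 20). Sections 9.1 to 9.3 are marked completed, and Section 9.4 names Arm E as the recommended combination. Section 9.7.3 still calls for pairwise differences in immune response rate among the optimal combinations at study conclusion.

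**The concern.** Table 15 treats D as if it went with A, E with B and F with C. No explanation is given, and it does not match what the pairs contain. Where IFA is ranked the least toxic single agent (orderings 1 and 2), the pair without IFA is ranked the least toxic pair. Where IFA is ranked the most toxic (orderings 4 and 6), that pair is ranked the most toxic. If effects combine without interaction, D belongs at the other end in all four.

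The fitted probabilities define the acceptable set, and hence the range of optimal combinations (Section 9.1) and the comparison set for Section 9.7.3. If no available ordering can place D correctly, the model can exclude a safe D or admit an unsafe one.

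**Working it through.** **1. Orderings against components.** If single agents rank x<y<z and do not interact, the pairs rank x+y < x+z < y+z.

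| Ordering | Singles | Pairs in Table 15 | Pairs from components | Match |
|---|---|---|---|---|
| 1 | A-B-C | D-E-F | E-F-D | no |
| 2 | A-C-B | D-F-E | F-E-D | no |
| 3 | B-A-C | E-D-F | E-D-F | yes |
| 4 | B-C-A | E-F-D | D-E-F | no |
| 5 | C-A-B | F-D-E | F-D-E | yes |
| 6 | C-B-A | F-E-D | D-F-E | no |

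E against F is right in all six; the discrepancy is always D. The missing orderings are A-B-C-E-F-D-G, A-C-B-F-E-D-G, B-C-A-D-E-F-G and C-B-A-D-F-E-G.

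**2. Scenarios.** In Tables 17 to 20 the true DLT rates rise from A to G every time (Scenario 2: 5, 6, 8, 22, 23, 25, 45%). All four truths follow ordering 1.

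**3. Reproducing the plan.** The design in Sections 9.2 to 9.6.1 was re-coded. Section 9.2.3 can be read in two ways while an acceptable arm has fewer than three participants: fill the short arms first, or randomise over all acceptable arms.

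| Scenario | 1 | 2 | 3 | 4 |
|---|---|---|---|---|
| Mean size, stated | 45 | 45 | 29 | 7 |
| Mean size, fill first | 44.3 | 43.8 | 29.4 | 6.1 |
| Mean size, all acceptable | 57.4 | 52.4 | 29.9 | 5.7 |
| Safety stops %, stated | 0.4 | 2.2 | 25.2 | 96 |
| Safety stops %, fill first | 0.3 | 3.0 | 23.6 | 98.4 |

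Filling first fits, so it is used below. Its largest selection gap is G in Scenario 1 (55% against 62% stated).

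**4. Case 1 (assumed rates): IFA drives toxicity and D is the only safe pair.** DLT for A to G 25/5/8/12/40/45/55%; immune response 40/40/40/70/60/60/80%. Three independent codings gave:

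| Trials | D recommended, Table 15 | D recommended, matching orderings used or added | Ratio |
|---|---|---|---|
| 2500 | 24% | 47% | 24/47 = 0.51 |
| 1000 | 22% | 42-43% | 0.51-0.52 |
| 600 | 25% | 40-44% | 0.57-0.63 |

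The Monte Carlo standard error is √(0.47×0.53/2500) = 1.0 point in the largest run and √(0.42×0.58/600) = 2.0 points in the smallest. D was called acceptable in 32-33% of trials with Table 15, against 61-66%.

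Five further assumed truths of this type compare Table 15 with the six component-matching orderings:

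| A/D/E/F DLT % | Table 15 | Matching | Ratio |
|---|---|---|---|
| 20/10/40/42 | 22.9% | 42.8% | 0.54 |
| 25/10/45/48 | 20.9% | 45.3% | 0.46 |
| 30/10/50/52 | 16.9% | 44.9% | 0.38 |
| 25/20/45/48 | 17.6% | 30.3% | 0.58 |
| 12/8/40/42 | 32.1% | 44.5% | 0.72 |

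In the second row the ten-ordering set gave 44.6%. The alternative reading of Section 9.2.3 shows the same pattern with larger losses (15% against 46% in that row), but it does not reproduce the plan's trial sizes.

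**5. Other assumed truths.**
- Case 2, IFA mild and D unsafe (DLT 3/12/18/45/15/22/50%; immune response 40/40/40/80/60/60/85%): unsafe D recommended 20-21% against 11-15%; safe E or F 28-32% against 40-43%.
- Three more IFA-mild truths, safe pair selected: 54.7 v 63.7%, 38.8 v 45.5%, 25.7 v 38.7%.
- PolyICLC or resiquimod driving toxicity: 41.3 v 47.1% and 40.8 v 46.1%.
- A truth following ordering 3, which is in both sets: 46.2 v 49.9%.
- All arms safe: 34.2 v 34.3%.
- The plan's Scenario 2: Zone 2 total 61 v 63%, so adding orderings costs nothing visible.

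**6. Could the completed Part 1 result change?** G is last in all ten orderings. If G's estimate is at most 33%, so is every other arm's under the selected ordering; this needs 0.45^θ ≤ 0.33, that is θ ≥ ln 0.33 / ln 0.45 = 1.39. G's final estimate is not given. Refits fixed E at 1/16 (Section 9.6.2) and G at 6 participants (Section 9.0), and assumed 4 to 6 participants on each other arm and 0 to 3 DLTs on each arm except E. With six or ten orderings the acceptable set was identical up to 3 total DLTs, counting the one on E. It can differ from 4 upward. E was never excluded up to 5.

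**The case against.** The arm contents alone require only that a single agent is no more toxic than a pair containing it, and a pair no more toxic than the triple. All six orderings respect that, and the plan calls its list a selection. A reader might infer that Table 15 contradicts the arm definitions. The documents do not support that reading: placing D by its components needs a no-interaction assumption that they neither state nor deny. This stands, so the four orderings are implausible without interaction and unexplained, but not impossible.

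Part 1 is finished. Part 2 is single-arm with a fixed sample size and its own sequential DLT boundary, so no future allocation depends on Table 15. Arm E had 1/16 DLTs. Section 9.0 sets G aside because resiquimod is unavailable and E enrolled more, and does not mention toxicity. This also stands: a reader might infer that the choice of Arm E is unsafe, and neither the reported data nor the refits support it.

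The Case 1 and Case 2 rates are assumptions. IFA-driven local toxicity is not far-fetched, since Section 5.4.2 expects chronic inflammation in every Montanide recipient and Section 7.4.3 cites 7% grade 3 ulceration in an earlier IFA arm. That does not establish the assumed rates.

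Finally, replacing prespecified tables after the data are in would be post hoc. That is right and shapes the fix.

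What the objection does not remove is the Section 9.7.3 comparison, which is still due and takes its arms from the fitted set. DLT counts by arm are not in the documents, so a change for arms other than E cannot be excluded.

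**Conclusion.** The point holds in a limited form. Unless the agents interact, four of the six orderings misplace D, the four matching orderings are missing, and Section 9.3 examined only truths that follow ordering 1.

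The size depends on the truth. Where IFA drives toxicity and D is the only safe pair, the chance of recommending D is roughly one half to two thirds of what matching orderings give (0.51 to 0.63 across the codings of Case 1; 0.38 to 0.72 over the five further truths). Elsewhere the loss is about 4 to 13 percentage points, and it is nil when all arms are safe. These figures rest on assumed rates and on the fill-first reading of Section 9.2.3. A general halving should not be inferred.

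For the completed Part 1 the practical question is narrow: does the acceptable set, and so the Section 9.7.3 comparison set, change when the missing orderings are allowed? On the assumed counts it does not up to 3 total DLTs and may from 4 upward. The choice of Arm E is not expected to change.

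**What to change.** - Keep the prespecified analysis with Tables 15 and 16 as primary for Part 1.
- Add a sensitivity refit of the final Part 1 DLT data, labelled post hoc, with the four missing orderings added to the six (ten in all) and the same working values along each.
- Report whether the acceptable set differs and, if so, give the Section 9.7.3 pairwise differences for both sets.
- State in Section 9.3 that the operating characteristics hold only for truths that follow ordering 1, or add one scenario whose truth follows a component-consistent ordering. If an interaction was assumed when Table 15 was drawn up, say so and give the reason.

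The cost is about a day of programming and a short text edit. No participants are needed and Part 2 conduct does not change. The downside is a small amount of post hoc analysis, which the label makes plain.

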#### 9.2.3 Combination recommendation:

Once the set of "acceptable" combinations is determined, the recommended combination will be based upon how many participants have been entered into the study to that point. If less than 3 participants have been treated on any acceptable dose, then the recommended combination for the next entered participant will be chosen at random from the acceptable combinations. If at least 3 participants have been treated at every acceptable combination, the recommended combination for the next participant entered is defined as the "acceptable" combination with the highest observed IRR. After each participant, a new recommended combination is obtained, and the next entered participant is allocated to the recommended combination. Part 1 of the trial will stop once sufficient information about the optimal dose range has been obtained, according to the stopping rules outlined in Section 9.6.1.

## 9.3 Statistical properties Part 1 (completed)

Simulation results were run (R package, pocrm) to display the performance of the design characteristics. For each scenario, 1000 simulated trials were run. Each table reports the true DLT probability at each combination, the true IRR at each combination, the percentage of trials in which each combination was recommended as the optimal combination, and the average number of participants treated in a simulated study.

#### 9.3.1 Scenario 1:

All true DLT probabilities are safe (i.e. less toxic than 33%) and one combination has the highest IRR. The true optimal combination is indicated in italicized bold type.

Table 17: Study Scenario 1

Zones		1		2			3
Combination	Α	В	С	D	Е	F	G
True DLT probabilities	1%	2%	5%	7%	11%	14%	20%
True IRR	35%	35%	40%	55%	60%	65%	80%
% optimal combination recommendation	0%	1%	1%	7%	10%	18%	62%
% participant allocation	8%	8%	9%	12%	14%	17%	33%

Average trial size: 45 participants (25th, 50th, 75th percentile = 40, 43, 48)

0.4% of simulated trials were stopped for safety

The overall toxicity rate was 11.8%. The overall IRR was 60.9%.

